Secondary outcomes will include: pre-analgesia pain score (P_o), post-operative pain score (P_{20}), patient intolerance to the procedure, postoperative voiding trial results (pass/fail), and post void residual (PVR) results at 2 week follow-up (measured in ml, pass/fail), and diagnosis of urinary tract infection (accepted clinical definition of acute cystitis or a positive urine culture) at 2 week follow-up. PVRs < 200ml at 2 week follow-up will be considered passing result [31].

Participants will also rate their level of satisfaction with pain control immediately after the procedure using a simple Likert scale. This will be a 4-level scale ranging from 'not at all satisfied,' 'slightly satisfied,' 'mostly satisfied,' and 'very much satisfied.'

Expected Results

Investigators believe that participants randomized to the B&O suppository group will experience less bladder pain (average pain) during the BoNT injection procedure than those that were assigned to the placebo group.

Study Type and Design

This study is a randomized, pilot trial. Clinical investigators and participants will be blinded to the randomization groups. Participants, whom have elected to receive BoNT injection therapy, will be randomized to receive either a placebo or B&O suppository prior to the procedure. Pain will be assessed prior to the procedure, during the procedure, and after the procedure.

Sample size

Sample size is calculated assuming the group receiving the B&O suppository reports an average intra-procedural pain (P_{10}) score of 4.5, and assuming the control group (placebo) reports an average intra-procedural pain (P_{10}) score of 8. The assumed standard deviation is 3. Based on a power of 0.8, the required sample size per randomization group is 13. The total sample size required to achieve a power of 0.8 for this pilot trial would be 26 (13 per group).

Randomization

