narcotics. The prescription will be provided to the compounding pharmacy, which will fill the prescription based on the pre-determined randomization scheme. The compounding pharmacy will document and deliver the pill canister matching the participant's ID number, to the clinic and provide it to the Principal Investigator to store in a locked medicinal refrigerator in a locked room until the day of the procedure. Prior to administering the suppository to the patient during the procedure, the Principal Investigator will open the pill canister and document the pill canister number and the number labeled on the suppository in the patient's medical record, and study documents. If unveiling the randomization for a participant is required, the Principal Investigator can call the data coordinator or the compounding pharmacy, and the coordinator or the lead pharmacist will reveal the participant's randomization assignment over the phone. Monthly meetings will be conducted to audit the enrollment and to ensure randomization procedures are conducted appropriately.

Statistical Analysis

Preoperative demographic variables including age, race, parity, body mass index (kg/m^2), menopausal status, smoking status, medical comorbidities, and indication for BoNT treatment (OAB vs. NDO) will be compared between active and placebo patients. Continuous variables will be compared using Student t-tests. Categorical variables will be described as frequency data (proportions & percentages) and compared using Chi-square or Fisher's exact test (when expected values in any cell are less than 5). Ordinal variables will be compared using Wilcoxon Rank Sum tests.

An intent-to-treat analysis approach will be used. Results for the active group versus the control group will be compared with paired t-tests if the data are normally distributed and with Mann-Whitney tests if the data are skewed. Regression modeling will be used to analyze the relationship between our primary outcome with the following predictor variables; active vs. placebo, indication for BoNT injection (OAB vs. NDO), demographic variables, and pain scores (before-during-after procedure). Interactions between variables will be assessed and, if significant, included in the model.

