Confounding variables will be included in the model if point estimates change by more than 20% with their inclusion. Continuous variables will be assessed for linearity and converted to categorical variables as indicated by model fit statistics (c-statistic, Deviance, Pearson, Hosmer-Lemeshow). Cochran-Armitage and Goodness of Linear Fit tests will be used to evaluate for linear trends between suppository treatment and our primary outcome.

All statistical analyses will be two-sided. P-value of less than 0.05 is considered to be statistically significant. An interim analysis will be performed one year after Institutional Review Board if the study has not completed data collection within one year. Results will not be given to participants.

Participants

Patients will be approached for participation once they have selected BoNT therapy for treatment of overactive bladder (OAB), neurogenic detrusor overactivity (NDO), or refractory interstitial cystitis (IC).

To be included in this study, patients must be 18 years old or older at the time of the informed consent discussion, have met clinical criteria under outside care or during the Principal Investigator's routine standard of care for BoNT injection therapy (failed initial medical management), and there must be no contraindication to BoNT therapy as outlined by drug manufacturer guidelines (Table 1). Patients will have elected to have the BoNT injection therapy prior to being offer enrollment into the study for either OAB, NDO, or IC.

Patients will be excluded for pregnancy, currently nursing a baby, age less than 18 years, or anticipated geographic relocation within the first 3 months following treatment. Patients will be excluded if the patient reports an allergy to morphine, belladonna, or opiates. Patients will also be excluded if participating in another research study. Individuals unable to provide informed consent or to complete two-week follow-up bladder testing (post-void residual) or data collection will also be excluded. Prior to randomization, a data coordinator will verify eligibility and completeness of baseline data.

Participants will be withdrawn or terminated from participating in the study by a clinical investigator if they fail to undergo the BoNT injection procedure and do not reschedule before the conclusion of the study.

[figure not shown]

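### Choosing covariates by a 20% change and interactions by significance can raise the adjusted test's false-positive rate from 5% to about 6–10% in this 26-patient trial

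*Combined protocol and SAP*

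**What the plan says.** The Statistical Analysis section of the combined protocol and SAP first plans a direct comparison of the two arms. It then plans a regression of the primary outcome on treatment, indication, demographic variables and pain scores.

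Two rules decide what else enters that regression:
- For covariates: "Confounding variables will be included in the model if point estimates change by more than 20% with their inclusion".
- For interactions: "Interactions between variables will be assessed and, if significant, included in the model".

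The error rate is set by "All statistical analyses will be two-sided" and "P-value of less than 0.05 is considered to be statistically significant".

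The section does not say which point estimates must move, in what order covariates are tried, which interactions are tested, or whether the two-group test or the regression is decisive. It fixes no adjustment set and gives no multiplicity control. The closing text of the Participants section promises suitable treatment of confounders but adds no rule.

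**The concern.** The 20% rule comes from observational work, where a shift in the exposure estimate can signal confounding. Under randomisation, a shift caused by a baseline covariate reflects chance imbalance. Selecting on it lets the observed data shape the model, while the p-value is calculated as if the model had been fixed beforehand.

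The threshold is relative, so the nearer the estimate is to zero, the smaller the shift that lets a covariate in. The search is therefore widest when there is no effect to find.

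Testing interactions for significance adds a second search. If an interaction with treatment is kept and covariates are not centred, the treatment coefficient is also no longer the average effect.

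At stake is the only planned adjusted estimate for the primary outcome, and whether its test keeps the stated 5% level.

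**Working it through.** **Inputs from the documents.** Difference 8 − 4.5 = 3.5 points, SD 3, 13 per arm (Sample size); 1:1 allocation (Randomization); two-sided 0.05 (Statistical Analysis).

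**Assumptions.** The section names eight baseline characteristics for the comparison of arms, including indication. Adding the two pain scores taken before injection (P0 and Pa) gives 10. Treating these as the regression candidates is a reading, so 1, 4, 8 and 10 were tried. No covariate strength is given, so one covariate was allowed to explain R² = 0, 0.3 or 0.5 of outcome variance. Point estimates were taken to mean the treatment estimate.

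**The plan's own figure.** The plan states "Based on a power of 0.8, the required sample size per randomization group is 13". The standard error of the difference is 3 × √(2/13) = 1.18, so the noncentrality is 3.5/1.18 = 2.97 on 24 degrees of freedom. Exact t-test power is 0.814 at 13 per arm and 0.780 at 12. The figure reproduces and is not in question.

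**Why selection is heavier near zero.** Adding baseline covariate Z changes the estimate by γ × (difference in mean Z between arms), where γ is the fitted slope. For a pure-noise covariate scaled to SD 1:
- the fitted slope has standard error of about 3/√24 = 0.61;
- the imbalance has SD √(2/13) = 0.39;
- a typical shift is therefore about 0.61 × 0.39 = 0.24 points.

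If the true effect is zero, an estimate one standard error from zero gives a threshold of 0.2 × 1.18 = 0.24, about the same as a typical noise shift. At the planned effect the threshold is 0.2 × 3.5 = 0.70. This agrees with nine-candidate simulations, in which about 3.4–4.0 covariates were kept under the null and about 0.4–0.6 at the planned effect.

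**Type I error.** Simulation of 13 per arm with a linear model, independent normal covariates, and covariates centred when interactions were added; 10,000 runs per row, Monte Carlo standard error about 0.002.

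| Candidates | R² | 20% rule, one at a time | 20% rule, forward | Forward + significant interactions |
|---|---|---|---|---|
| 1 | 0 | 0.052 | 0.052 | 0.053 |
| 1 | 0.3 | 0.045 | 0.045 | 0.047 |
| 1 | 0.5 | 0.040 | 0.040 | 0.042 |
| 4 | 0 | 0.064 | 0.065 | 0.069 |
| 4 | 0.3 | 0.049 | 0.050 | 0.054 |
| 4 | 0.5 | 0.042 | 0.043 | 0.048 |
| 8 | 0 | 0.073 | 0.080 | 0.088 |
| 8 | 0.3 | 0.056 | 0.064 | 0.072 |
| 8 | 0.5 | 0.050 | 0.060 | 0.064 |
| 10 | 0 | 0.076 | 0.088 | 0.096 |
| 10 | 0.3 | 0.061 | 0.076 | 0.084 |
| 10 | 0.5 | 0.054 | 0.069 | 0.076 |

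One pre-specified covariate gave 0.047–0.053 throughout.

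A further run used nine candidates, all normal or mixed binary and continuous, with pairwise correlation 0 or 0.2. It gave 5.7–8.2% (selection at once) and 6.8–8.8% (stepwise), against 4.2–5.4% for two fixed covariates. The inflation does not depend on independent normal covariates.

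**Interactions.** The chance of at least one falsely significant treatment-by-covariate interaction is 1 − 0.95⁸ = 0.34 with eight tests and 1 − 0.95¹⁰ = 0.40 with ten. Simulation under the null gave 0.33–0.34 and 0.39–0.40.

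**Power at 3.5 points, 8–10 candidates, 20% rule against one pre-specified covariate** (3,000 runs, standard error up to 0.007):
- R² = 0: 0.79–0.80 against 0.79.
- R² = 0.3 (correlation √0.3 = 0.55): 0.85–0.87 against 0.91–0.92.
- R² = 0.5: 0.91–0.93 against 0.975.

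With two fixed covariates and nine candidates, fixed pair against rule: 0.89 against 0.85 at correlation 0.5, no difference at 0.3, and about 2 points lower at 0 (1 to 4 points across the covariate structures tried).

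**The case against.** The strongest reply is that the consequence is limited. The plan has a separate two-group comparison that neither rule touches, the null hypothesis in Study Objectives is a difference in mean change, and the sample size is for two means. The regression may be meant as descriptive, in what Study Type and Design calls a pilot trial. This stands in part. A reader might infer that the trial's main result is tested at an inflated level, and the documents do not support that. But they do not rank the two analyses either, so nothing prevents a significant result from the selected model being presented as the finding.

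The inflation is also modest and depends on assumptions. With one to four candidates and a prognostic covariate, the 20% rule is at or below 5%. This stands, although the section's own list points to 8–10 candidates.

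A reader might also infer that the rule always costs power. It does not. The outcome is already a change score (P10 − Pa), so its correlation with P0 is unknown and may be small. When R² = 0.5 was spread over three covariates, the rule had more power (0.89–0.91) than adjusting for one of the three (0.86–0.87).

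Finally, the 33–40% chance of a false interaction might be taken as the error rate for the treatment effect. It is not. It assumes that every treatment-by-covariate term is tested, whereas the plan refers only to interactions in general. With centred covariates the treatment coefficient remains the effect at average covariate values.

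**Conclusion.** The concern holds for the adjusted analysis. With about 8–10 candidates, the nominal 5% type I error of the adjusted treatment test becomes about 5–9% from the 20% rule alone and about 6–10% once significant interactions are also added. With four or fewer candidates the inflation is small or absent.

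These ranges rest on reading point estimates as the treatment estimate, and on candidate counts and covariate strengths that the documents do not give. The unadjusted comparison and the 13 per group are unaffected.

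Type I error is the reason to change the rule; power is not. Fixing the model gains about 3–6 points over the rule if the chosen covariate correlates about 0.5 with the outcome. Otherwise power is generally unchanged or falls by about 2 points, and the rule can come out ahead where prognosis is spread over several covariates.

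**What to change.** Replace both selection rules with one adjusted model, stated in advance and fitted whatever imbalance is observed: treatment, pre-dose pain (P0) and indication. Code indication to include interstitial cystitis as well as overactive bladder and neurogenic detrusor overactivity; the analysis section names only the last two, although the Participants section admits all three. P0 is suitable because it is taken before the suppository, whereas Pa is taken 40 minutes after it.

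State that the unadjusted two-group comparison of change in pain is the primary test and that the adjusted model is supportive. Label all other covariates and all interactions exploratory and keep them out of that model.

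The cost is wording only; sample size, data collection and conduct do not change. There are two small downsides. An unlisted imbalance can be addressed only in a sensitivity analysis, and the adjusted model loses a little power if the chosen covariates turn out not to be prognostic.

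### Continuous covariates in the regression of the pain outcome may be categorised on unspecified fit statistics; in 26 patients the effect on the adjusted treatment test ranges from negligible to about 13 power points, depending on how the rule is read

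*Combined protocol and SAP*

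**What the plan says.** The Statistical Analysis section of the combined protocol and SAP plans two things for the primary outcome. The first is a comparison of the two arms by t-test or Mann-Whitney test, without covariates. The second is a model: "Regression modeling will be used to analyze the relationship between our primary outcome with the following predictor variables". The predictors listed are treatment, indication, demographic variables and pain scores. Age and body mass index appear among the demographic variables earlier in the same section.

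For that model the plan adds: "Continuous variables will be assessed for linearity and converted to categorical variables as indicated by model fit statistics". Four statistics follow in parentheses: c-statistic, deviance, Pearson and Hosmer-Lemeshow. The plan does not say how large a departure triggers conversion, where the cuts fall or how many categories result.

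The Sample size section describes a plain difference in two means and states "Based on a power of 0.8, the required sample size per randomization group is 13".

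**The concern.** In a randomised trial, covariate adjustment earns its place by removing outcome variance. Cutting a covariate whose effect is roughly linear into groups throws away the information within each group. It also replaces one slope with several indicator columns, which in 26 patients will be unevenly spread over the arms by chance. Both weaken the adjusted treatment test.

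The decision is also made on the outcome data. Two analysts following the sentence faithfully could fit different models and report different p-values for treatment. Some selection rules also raise the false-positive rate. At stake are the power and the error rate of the adjusted treatment test on the primary outcome.

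**Working it through.** **Inputs from the plan.** Active arm "reports an average intra-procedural pain (P_{10}) score of 4.5"; placebo arm "reports an average intra-procedural pain (P_{10}) score of 8"; so the difference is 3.5. SD 3, 13 per arm (Sample size). "All statistical analyses will be two-sided", and "P-value of less than 0.05 is considered to be statistically significant" (Statistical Analysis).

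**Inputs assumed.** The plan gives no covariate strengths or shapes and no conversion rule. The runs below use three independent normal covariates, one related linearly to outcome with correlation r and the other two unrelated. The planning difference and SD, which the plan states for the mid-procedure score, are applied to the outcome being modelled.

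**1. The plan's own figure.** Noncentrality δ = 3.5 / (3 × √(2/13)) = 2.97 on 24 df. Exact two-sided t-test power is 0.814 with 13 per arm and 0.780 with 12. The stated 13 is reproduced, without covariates.

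**2. Degrees of freedom alone.** Keeping δ fixed and removing only residual df, power is 0.814 (0 covariate df), 0.810 (3), 0.803 (6) and 0.794 (9). This cost is small, and a median split uses the same 1 df as a slope.

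**3. Where the larger loss comes from.** If k covariate columns are pure noise, they explain on average k/25 of the treatment indicator by chance. Approximate power is then Φ(δ√(1 − k/25) − t), with t the 0.975 quantile on 24 − k df.
- Three linear terms, k = 3: 2.97 × √0.88 = 2.79; t = 2.08; Φ(0.71) = 0.76.
- Tertiles, k = 6: 2.97 × √0.76 = 2.59; t = 2.10; Φ(0.49) = 0.69.
- Quartiles, k = 9: 2.97 × √0.64 = 2.38; t = 2.13; Φ(0.25) = 0.60.

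These agree with the r = 0 row below to within 0.01. When r is above 0, lost covariate information adds to this.

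**4. Simulated power of the adjusted treatment test, three covariates.** The three columns of fixed forms used 2,000 trials per cell. The last column takes quartiles for a covariate whenever deviance is lower than with the linear term.

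| r | Linear | All tertiles | All quartiles | Quartiles if deviance lower |
|---|---|---|---|---|
| 0 | 0.76 | 0.68 | 0.60 | 0.63 |
| 0.3 | 0.79 | 0.71 | 0.63 | 0.67 |
| 0.5 | 0.85 | 0.76 | 0.69 | 0.74 |
| 0.7 | 0.96 | 0.86 | 0.81 | 0.89 |

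**5. Three readings of the trigger, each against always-linear.**
- *Lower deviance.* Losses are 0.76 − 0.63 = 0.13, 0.79 − 0.67 = 0.12, 0.85 − 0.74 = 0.11 and 0.96 − 0.89 = 0.07. Roughly 75 to 90% of covariates are converted although none has a curved effect, because unpenalised deviance favours the form with more terms. With one covariate the loss is 1 to 3 points.
- *Lowest AIC among linear, tertiles and quartiles.* Power stays within about 1 to 2 points. Type I error is about 0.08 with three covariates (3,000 null trials, Monte Carlo error about 0.5 points).
- *Tertiles only if a quadratic term has p<0.05.* The loss is 1.2 points or less in every scenario run, including truly curved and step-shaped effects (3,000 trials per cell). Type I error is about 0.05.

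**6. When a split helps.** If the true effect is a step at the median with correlation 0.7, a two-group split has power 0.94 against 0.92 for a linear term with one covariate, and 0.91 against 0.88 with three.

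**The case against.** The strongest objection is that the plan converts only after a linearity check. Losses computed by converting every covariate (8 to 10 points for tertiles and 15 to 16 for quartiles in the table) therefore describe a rule the plan does not contain. That stands, and those columns are shown only as a limit. It does not follow that conversion is rare. The curvature-test trigger is as much an assumption as any other, while deviance is a statistic the plan names, and simply comparing it makes conversion the usual outcome.

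A reader might also infer that the trial's stated power of 0.8 is lost. The documents do not support this. The sample size is for a two-group difference in means, that comparison is listed separately from the regression, and the categorisation sentence leaves it untouched. Nor is falling below 0.8 peculiar to categorising: three linear terms already give 0.76 at r = 0 and 0.79 at r = 0.3, a matter of which covariates are chosen. With one covariate at r = 0.5, even forced quartiles (about 0.84) beat the unadjusted test.

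A loss of degrees of freedom might seem the main mechanism. Step 2 shows that it is not.

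Finally, the c-statistic and Hosmer-Lemeshow test belong to models for a binary outcome, whereas the Outcomes section defines a numeric difference in pain scores. That is a separate defect in the same sentence. It leaves the trigger still less determined.

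**Conclusion.** The point holds for the regression of the primary outcome, which serves here as a supporting analysis. Its size depends on a rule the plan leaves open: about 7 to 13 power points if deviance is compared with three covariates, 1 to 3 with one; about 0.08 type I error with little power loss if AIC is used; about 1 point of power or less under a strict curvature test. These figures rest on the planning effect, on covariates that are truly linear or null, and on the assumed number of covariates. The spread across readings is itself the reason to fix the form in advance. The unadjusted comparison, and so the justification for 26 patients, is unaffected.

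**What to change.** Replace the categorisation sentence in the Statistical Analysis section with:

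> Continuous pre-treatment covariates included in the regression enter as linear terms and are not categorised; a prespecified sensitivity analysis adds a quadratic term for each.

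This removes the data-driven trigger and leaves open which covariates are included, which is a separate question. It costs one sentence and needs no new data. The downside is slightly less efficient adjustment when a covariate's effect is truly non-linear, about 2 to 3 power points for the step effect in step 6 of the working. Randomisation keeps the treatment estimate valid in that case.

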Overactive bladder (OAB) and urge urinary incontinence (UUI) affect 17% of women in the United States [1]. The economic burden of these conditions has been estimated at well over \$24 billion and is expected to increase to nearly \$82.6 billion in 2020 due to the aging population [2, 3]. These costs are largely due to the routine management of the symptoms (i.e. pads). Treatment costs account for a mere 14% of the overall cost. Cost reduction measures may include increasing access to diagnosis and treatment of OAB. Furthermore, the devastating impact on patients who suffer from OAB and UUI are well established. Clear associations with depression, sleep disorders, sexual dysfunction, and decreased quality-of-life scoring on validated surveys have all been observed in epidemiologic studies [4].

OAB is defined as urgency, with or without urge incontinence, usually with frequency and nocturia [16]. This affects up to 17% of women. The mechanisms contributing to urge incontinence include intrinsic malfunction of detrusor (bladder wall muscle) activity, overstimulation of detrusor muscle by acetylcholine, sensory urgency caused by abnormal sensory processing, or abnormal neuronal input to the detrusor. First line treatment involves bladder training, with the addition of oral anti-muscarinic agents if needed. These oral therapies improve symptoms and quality of life, with the NNT of 5-9 [17]. Albeit effective, these medications have reportedly poor adherence due to side effects with as many as 83% of patients discontinuing medication within the first 30 days. Second-line management includes BoNT intravesical injections, percutaneous posterior tibial nerve stimulation, and percutaneous sacral nerve stimulation. BoNT is one of the safest, least invasive, and effective options for refractory OAB [18].

Neurogenic bladder (NB), also known as neurogenic detrusor overactivity (NDO) is the urodynamic finding of uncoordinated bladder contractions. Those most commonly affected are young males with spinal cord injury and young females with multiple sclerosis. Of the estimated 273,000 people in the US with spinal cord injury, 81% experience urologic symptoms [19]. Additionally, 50-90% of persons with MS; 50% of persons with diabetic neuropathy; 24% of those with brain tumors; and 50% of patients with spinal stenosis will experience NB [20]. Among cerebrovascular accident sufferers, 8-11% will experience NB symptoms [21]. For NB patients who are able to empty their

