valid and reliable measure of pain intensity [30]. The primary outcome of our study will be determined by the patient experience objectified with the NRS. The overall goal of this study is to improve the patient experience with cost-effective evidence-based treatment.

Research Plan and Design

Study Objectives

The primary objective is to determine the effectiveness of B&O suppositories in decreasing bladder injection pain at time of BoNT injection.

Our null hypothesis: Among patients given standard analgesia for BoNT treatment of overactive bladder (OAB), neurogenic detrusor overactivity (NDO), or refractory interstitial cystitis (IC), there is no difference in bladder injection pain scores with the addition of B&O suppository when compared to placebo suppository.

H₀: Mean Δ pain during procedure in active suppository group = mean Δ pain during procedure in placebo suppository group.

Change in pain (*Mean Δ pain*) is considered to be the difference in pain from the baseline pain level after analgesia, and after the first 10 injections.

Outcomes

The primary outcome will be bladder injection pain. Pain will be measured using numeric rating scales (NRS). Participants will score their preoperative baseline pain level when they check into the clinic for their procedure (P_o). Participants will report pain 40 minutes after administration of standard analgesia and suppository (just prior to bladder injection) (P_a). This will allow calibration of our primary outcome for patients with higher levels of baseline pain not related to the procedure (using themselves as controls). They will then be asked to rate bladder pain after the first 10 injections (midpoint of the procedure) intraoperatively (P_{10}). After the procedure is completed, which would be after 20 injections, the patient will again be asked to report their pain (P_{20}).

The operational definition of our primary outcome will be calculated difference in NRS pain score prior to procedure (P_a) and midway through procedure (P_{10}): Δ pain (intraoperative pain score – preoperative pain score).

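### NDO patients are eligible with no check that they can feel the bladder; any participant who cannot would cost power and precision in a 26-person pain trial

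*Combined protocol and SAP*

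**What the plan says.** **Objective and outcome.** Under Study Objectives: "The primary objective is to determine the effectiveness of B&O suppositories in decreasing bladder injection pain at time of BoNT injection". The Outcomes section defines the primary outcome as P_10 minus P_a. P_10 is the NRS score after the first ten injections, and P_a is the score after analgesia, just before the injections.

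**Eligibility.** Participants states: "Patients will have elected to have the BoNT injection therapy prior to being offer enrollment into the study for either OAB, NDO, or IC". The exclusions cover pregnancy, nursing, age, relocation, other research and drug allergy. The one closest to the ability to give data is: "Individuals unable to provide informed consent or to complete two-week follow-up bladder testing (post-void residual) or data collection will also be excluded". Table 1 lists infection, hypersensitivity, retention and residual volume, self-catheterisation, antiplatelet and anticoagulant therapy, and antibiotic compliance. Table 4 lists the baseline data. None of these mentions bladder sensation.

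**Who has NDO.** The Background says: "Those most commonly affected are young males with spinal cord injury and young females with multiple sclerosis". It also cites diabetic neuropathy among the conditions associated with neurogenic bladder.

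**Sample size.** The active arm "reports an average intra-procedural pain (P_{10}) score of 4.5", and the calculation continues by "assuming the control group (placebo) reports an average intra-procedural pain (P_{10}) score of 8". The SD is 3, power is 0.8 and there are 13 per group.

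**Randomization and Statistical Analysis.** Allocation is 1:1 in blocks, with no stratification stated. Analysis is by intent to treat. A regression includes indication (OAB vs. NDO), and interactions are assessed.

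**The concern.** The trial measures only how much the needle hurts, so a participant informs the primary comparison only if the injections can be felt. Someone with no bladder sensation would report about 0 at P_a and about 0 at P_10 with either suppository. The data-collection exclusion does not remove that person, because a score of 0 is a complete answer. Intent to treat keeps the score in the analysis. Because sensation is not among the listed baseline items, such a participant could not be clearly identified afterwards.

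With 13 per arm, each such score pulls the expected difference towards zero and widens the spread. At stake is the trial's ability to detect the 3.5-point difference for which it was sized.

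**Working it through.** **Inputs.** From Sample size: means 8 and 4.5, SD 3, 13 per arm. From Statistical Analysis: two-sided 0.05. The number k of participants without sensation is not in the documents; k = 1 to 4 is an assumed range, and k = 0 is possible.

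**1. The plan's own figure.** Difference 8 − 4.5 = 3.5; standardised, 3.5/3 = 1.17. The exact two-sample t-test gives power 0.780 at 12 per arm and 0.814 at 13. The stated 13 per arm reproduces.

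**2. Effect on the difference.** If k of the 26 score 0 and are placed at random, and the stated means apply to the rest, the expected difference is 3.5 × (1 − k/26). For k = 1 this is 3.37; for k = 4 it is 2.96.

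**3. Effect on the variance.** With a share f at 0, an arm with mean m has variance (1 − f) × 9 + f(1 − f) × m². For f = 10%:
- placebo: 8.1 + 0.09 × 64 = 13.86
- active: 8.1 + 0.09 × 20.25 = 9.92
- pooled SD: √11.89 = 3.45, with difference 3.15

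Power at 13 per arm is then 0.61. Holding the SD at 3 would give 0.73, so the added variance accounts for more than half of the loss.

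**4. Power by count, unadjusted t-test (simulation).**

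| k | Raw P_10 | P_10 − P_a, mean P_a = 2 |
|---|---|---|
| 0 | 0.81 | 0.81 |
| 1 | 0.72 | 0.76 |
| 2 | 0.64 | 0.70 |
| 3 | 0.56 | 0.65 |
| 4 | 0.50 | 0.61 |

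The last column is on the scale of the primary outcome, with means 8 − 2 = 6 and 4.5 − 2 = 2.5. It assumes the same P_a in both arms and an SD of 3 for the change; the documents give neither. The raw P_10 column is the case of P_a = 0, so the two columns span an assumed mean P_a of 0 to 2. Simulated values are good to about 0.01.

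**5. Enrol or leave out.** On raw P_10, 24 participants with sensation (12 per arm) give power 0.78. The same 24 plus two without sensation give 0.64. Leaving them out gains power even if they are never replaced.

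**6. What the planned regression recovers.** Adding an NDO term, on raw P_10, for k = 1 to 4:
- if every NDO participant lacks sensation: 0.80, 0.78, 0.75, 0.74
- if half do: 0.75, 0.68, 0.62, 0.55

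**7. Type I error.** With both means at 8 and k = 0 to 4 zeros placed at random, the t-test rejects in 0.049 to 0.054 of trials.

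**The case against.** **The premise comes from outside the documents.** The protocol never says that NDO patients lack sensation. This stands: the link is general clinical knowledge and no frequency can be taken from the text. A reader might infer from the Background sentence that the trial will recruit many young men with cord injury. The documents do not support that. The sentence is general epidemiology, the site is a women's pelvic surgery clinic, and parity and menopausal status are baseline variables. The gap in the criteria remains.

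**The means may already include such patients.** Sample size gives 8 and 4.5 as the average each group reports, which can be read as covering everyone enrolled. On that reading, adding zeros counts them twice. The documents do not settle this. If four of 26 scored 0, a placebo mean of 8 overall would need 8 × 26/22 = 9.45 among the rest, so that reading becomes strained as k grows. It is quite possible for k = 1 or 2.

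**The regression handles it.** It does so in part. Indication is a proxy that groups NDO patients with and without sensation, and a main-effect term does not restore a lost contrast. The unadjusted comparison also stays in the plan.

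**An uneven split could mimic a drug effect.** A reader might infer this, since with k = 2 both fall in one arm with probability 2 × 78/325 = 0.48. On raw P_10, power is then 0.29 if both are in placebo and 0.91 if both are in active. But this is chance imbalance under randomisation, which the test already allows for: type I error stays near 0.05.

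**A mixed population is a legitimate question for a pilot.** It is, and the null hypothesis names all three indications. Restricting to patients with sensation narrows that question, so the change must be stated openly.

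**Conclusion.** The point holds as a cheap improvement to eligibility. NDO patients are eligible, and nothing in the criteria or the listed baseline data addresses whether they can feel the injections. Any participant who cannot would add a near-zero change in either arm.

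The cost is power and precision, not bias. Unadjusted power falls from 0.81 to between 0.72 and 0.76 with one such participant, and to between 0.50 and 0.61 with four. This range rests on three assumptions: k is 1 to 4, the sample-size means describe patients with sensation, and mean P_a lies between 0 and 2. If k is 0, nothing is lost. The NDO regression term reduces the loss, more so when NDO status tracks sensation closely.

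Two stronger conclusions are not supported. The figure of 0.50 is the low end of an assumed range for an unadjusted test on raw P_10, not the expected power of the trial. Nor would a null result be uninterpretable: it would be a less precise estimate of the average effect in the mixed population.

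**What to change.** In Participants, add one exclusion: patients with known absent bladder sensation, established by history or existing records. State with the objective that the conclusion applies to patients with bladder sensation. OAB patients, IC patients and NDO patients with sensation stay eligible, and no treatment or procedure changes.

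The cost is one eligibility line, one screening question, a slightly narrower NDO population and the loss of any candidates who could not inform the pain comparison. If the investigators prefer to keep the wider population, the minimum is to record bladder sensation at baseline so that its effect on the result can be examined.
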